- Being deemed unable to comply with the study protocol (either self-selected or by indicating during screening that s/he could not complete all requested tasks)
- Participation in other hypertension-related clinical trials
- Have significant psychiatric comorbidity or reports of substance abuse (as documented in the EHR)
- Plan to discontinue care at the practice within the next 15 months

Clinic and nonclinical staff Eligibility Criteria

Inclusion criteria:

- Primary care provider (MD/DO, NP), Nurse, Medical Assistant, or administrative staff employed at the participating practices and interacts with at least five patients with a diagnosis of hypertension.

Exclusion criteria:

- Refuse to participate.

Number of Participants

Implementation Phase

Clinical and nonclinical staff:

Surveys and interviews: 204

Patients:

Surveys: Randomly selected sample of 70 patients from each of the 10 participating primary care clinics (n=700). We will also be selecting a sample of 300 patients across participating clinics who met the eligibility criteria but did not participate in ALTA to participate as a control group.

Interviews: A randomly selected subsample of 30 patients with uncontrolled HTN who participated in ALTA (n=700)

Table of Contents

1 – Introduction	9
1.1 Introductory Statement	9
2 – Background	10
2.1 Background/prevalence of research topic	10
3 – Rationale/Significance	11
3.1 Problem Statement	11
3.2 Purpose of Study/Potential Impact	11
3.3.1 Potential Benefits	12
3.3.2 Potential Risks	13
4 – Study Objectives	15
4.1 Hypothesis	15
4.2 Primary Objective	15
4.3 Secondary Objectives (if applicable)	15
5 – Study Design	16
5.1 General Design	16
5.1.1 Study Duration (if applicable)	17
5.1.2 Number of Study Sites	17
5.2.1 Primary Outcome Variables	17
5.2.2 Secondary and Exploratory Outcome Variables (if applicable)	17
5.3 Study Population	19
5.3.1 Number of Participants	19
5.3.2 Eligibility Criteria/Vulnerable Populations	20
6 – Methods	22
6.1 Description of PF implementation strategy	22
6.1.1 Usual Care (UC) Phase	22
6.1.2 Pre-implementation phase	22
6.1.3 Description of Implementation phase	23
6.1.4 Selection of Instruments/Outcome Measures	24
6.1.5 Intervention Administration	31
6.1.6 Reaction Management	32

6.2.1 Efficacy	32
6.2.2 Safety/Pregnancy-related policy	33
6.2.2.1 Adverse Events Definition and Reporting	33
6.2.3 Pharmacokinetics (if applicable)	33
6.2.4 Biomarkers (if applicable)	33
6.3.1 Study Schedule	33
6.3.2 Informed Consent	34

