As part of the ongoing Quality Improvement evaluation process, the study team will use the data from the workbench report to:

- Identify missed opportunities (patients who were eligible but were not enrolled in the program) and generate ideas for improvement with the sites (e.g., discuss these missed opportunities in daily huddles). Data will be presented to sites in an aggregated form.
- Collaborate with MCIT to refine the Epic workflows based on-site feedback and data from the workbench reports (e.g., smartest for MDs to place the MyChart Home Blood Pressure monitoring not firing)
- Complete PDSA (Plan-Do-Study-Act) cycles with the ALTA QI Champions at the sites to develop shared goals for improving ALTA implementation.

Since the data needed to provide performance feedback to the sites is in Epic, exported data will be password protected and stored in a study folder shared drive. Only study team members will have access to the data.

BP control, the major secondary outcome, will be defined as SBP <140 and DBP <90 mmHg. BP control will be assessed using the mean of the last two measurements recorded in the EHR during each of the pre-intervention and post-intervention study periods (baseline and 12 months). BP readings will be extracted from patients' EHR by trained RAs. We will use the last two recorded measures to reduce variability associated with multiple BP measurements being taken by different clinic staff. We will also examine the proportion of patients with BP control <130/80 mmHg in exploratory analyses to provide preliminary data on BP control rates of hypertensive patients when considering the new guidelines. We will also explore mean change in systolic and diastolic BP based on the mean of the last two recorded BP readings in the EHR during the pre- and post-intervention periods.

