6.3.4 Recruitment, Enrollment and Retention

Practice clinical and non-clinical staff will be recruited through study team attendance at the monthly staff meetings, email communications that describe the project including the overarching goals and what is expected of participants, and in-person or virtual meetings with the practices.

We will recruit approximately 500 patients across the practices who meet the following eligibility criteria (described above). Several strategies will be used to maximize the number

of eligible patient participants recruited per practice as described below. Signed informed consent will be obtained from participants who meet the study eligibility criteria.

Since this is a clinic wide initiative, we are broadening our eligibility criteria to include patients of all race and ethnicities, and not be exclusive to Latinx patients (this is also reflected in the change to our project name). We will still recruit a random sample of 70 patients per clinic that receive care in the 10 safety-net practices to participate in the surveys to assess our tertiary outcomes. Of this sample, 30 will be randomly selected to participate in an exit interview. Patients will be randomly selected from a list of patients who receive care in the clinics and have been exposed to the ALTA project. The same recruitment strategies will be employed to recruit 300 patients who receive care in the clinics and met eligibility for ALTA but did not ultimately participate in the project. All patients will provide written informed consent prior to participating in the study.

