6.3.6 End of Study and Follow Up

Patient Consent at baseline: During this visit, trained RAs will use a standardized form to screen patients based on the study's inclusion and exclusion criteria. Verbal consent will be obtained prior to beginning the eligibility screening. Only patients that meet all eligibility criteria will then complete the consent procedures, during which a trained RAs will describe the study in easy-to-understand language. If the patient remains interested, the RA will obtain written informed consent in the patient's preferred language (English or Spanish). The patient will then complete a demographic questionnaire, validated surveys on patient trust, relationship commitment and anxiety, and have their medical chart reviewed by a trained RA. This visit should take 15 minutes.

Final study visit at 12-Months (post randomization): At 12 months, trained RAs will repeat the chart review procedures for consenting patients, in accordance with IRB and

HIPAA regulations. Patients will also complete the same measures on patient trust, relationship commitment and anxiety. In addition, we will conduct semi-structured interviews with a random sample of 30 patients with uncontrolled HTN about their experiences with ALTA over the past 12 months and its impact on the patient-provider relationship, as well as recommendations for improvements. This visit will take approximately 60 minutes.

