6.4.2 Sample Size Considerations

Power calculations are based on the clinical outcome of BP control using our prior work implementing the ALTA model in a community-based clinic. In the former trial, we found a significant improvement in attainment of BP control at 6 months among patients randomized to the intervention group compared to the UC group (51% vs. 29%, $p=.03$). We expect a similar group difference of a 20% increase in BP control between the implementation and UC phases in the current study. Calculations of achieved power were estimated with a stepped-wedge design using Power Analysis and Sample Size (PASS) software program. The power calculations show that we can recruit 10 sites and 700 patients and have at least 80% power to detect a more conservative 15% difference in BP control between the UC and implementation phases for intraclass correlation coefficients (ICCs) ranging from 0.01 to 0.05. Using our original estimate of a 20% difference in BP control, we would have over 90% power to detect a difference between the UC and implementation phases with 10 sites and 700 patients.

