Following the NIH Best Practices for mixed methods research, we will construct a joint display that integrates the qualitative themes with the quantitative data to create a composite measure of implementation fidelity based on the five dimensions outlined above. Should the data be divergent, we will assign higher credence to the qualitative data because it provides richer explanation about participants' behaviors. We will also explore the association between implementation fidelity and the clinical outcomes. This analysis will be accomplished with a multilevel MANOVA (unstructured covariance matrix across two time points: baseline and 12 months). The analysis will have one within person factor — Time (baseline and 12-month coded naturally as months (0 and 12)) and one primary between-

patient factor (Randomization Group dummy coded as 0 = UC and 1 = PF). We will use the composite measure of implementation fidelity to predict changes in BP control and medication adherence at 12 months. We will use a 3-level analytic model to accounting for nesting in the data (observations nested within subjects nested within practices). Multilevel modeling software (SAS, Version 9, PROC MIXED) will be used to compute full information maximum likelihood (FIML) estimates of the model parameters. The PROC MIXED procedure will use an error structure that allows for the possibility of group differences in (a) the error variances at 12 months; and (b) the serial correlations of the baseline with the 12 month outcomes. The primary test is the treatment X time interaction, and the resulting F-test will provide the primary "intent to treat" test of the hypothesis. If this is statistically significant at the two tailed $\alpha=.05$ level, for ease of interpretation, we will estimate and report the magnitude of the treatment effect, with 95% CI for fidelity. Covariates will be included as necessary in adjusted analyses. All tests will be 2-sided, 0.05 level tests.

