6.4.3.2 Secondary Objectives Analyses

The effect of PF on BP Control

Our main clinical outcome is the proportion of patients with adequate BP control (<140/90 mmHg) at 12 months in the implementation vs. UC phase. BP control will be treated as a dichotomous outcome variable in this analysis; any patients with missing follow-up BP data will be assumed to have inadequate BP control. To examine the difference in BP control rates between the implementation and UC phases, we will utilize a generalized linear mixed model (GLMM) to assess the PF effect. A Poisson regression model will be used to predict BP control specifying a fixed effect for time, a fixed effect for treatment and a time by treatment interaction. Random effects will be specified for person and practice to account for the clustered nature of the dataset (observations within person and people within practices). As a sensitivity analysis, we will also assess an alternate definition of BP control (< 130/80 mmHg) indicated by the new hypertension guidelines. In exploratory analyses, will examine the intervention effect on BP reduction at 12 months, treated as a continuous variable. An additional sensitivity analysis will be conducted using GLMM to evaluate the effect of PF on BP reduction. We will test the treatment X time interactions in a random effects linear regression model to determine the time-specific differences BP reduction attributable to PF at the end of the implementation phase.

Randomization of the stepped-wedge design should obviate the need for adjustment, but in the case of imbalanced in baseline covariates; these will be included as necessary in adjusted analyses. All tests will be two-sided with $\alpha=0.05$ for comparison between the implementation and UC phases. Maximum likelihood estimation of mixed-effects models will be used to account for missing data; in the context of a mixed-effects model, this is equivalent to an assumption of data that are missing at random (MAR); we will conduct sensitivity analyses assessing this assumption. We will also compare participants with and without missing values with respect to baseline and practice characteristics. If differential patterns emerge, we will consider the use of multiple imputation and/or inverse probability weighting to adjust for missing data. Analyses will be conducted using Stata, SAS, and R.

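### Section 6.4.3.2 defines no analysis population for BP control and PDC; if the 700 ALTA-exposed patients are analysed, the result is an effect among participants, not the effect of PF on eligible patients of the practices

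*Combined protocol and SAP*

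**What the plan says.** Section 5.1 states the clinical aim: PF against usual care on BP control and medication adherence, in 10 practices and their patients with uncontrolled hypertension who are non-adherent. Section 6.4.2 powers this on BP control: "The power calculations show that we can recruit 10 sites and 700 patients and have at least 80% power to detect" a 15-point difference. Section 6.4.3.2 gives the models for BP control and PDC but names no analysis population.

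Two places describe the 700 as people who received ALTA:
- Synopsis, Number of Participants: "A randomly selected subsample of 30 patients with uncontrolled HTN who participated in ALTA (n=700").
- Section 6.3.4, on the 70 per clinic: "Patients will be randomly selected from a list of patients who receive care in the clinics and have been exposed to the ALTA project".

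Two places point to a wider or earlier set:
- Section 6.1.1 has eligible patients recruited during usual care, before ALTA exists at the site.
- Section 6.1.4, under Secondary Outcomes, requests an EHR report with BP readings and PDC for hypertensive patients of the 10 practices. One stated use is to find "patients who were eligible but were not enrolled in the program".

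A further 300 eligible patients who did not take part in ALTA form a control group. They are described for the patient-provider relationship (Section 5.3.1) and appear in the tertiary model (Section 6.4.3.3). Section 6.3.4 also gives a recruitment figure of about 500, and a separate target of 300 for the recruitment-methods comparison.

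**The concern.** What is randomised is when a practice crosses over. The matching comparison takes all eligible patients of the practice in each phase, whether or not they accept coaching. A sample drawn from ALTA-exposed patients is defined by something that happens after crossover. It answers how BP control changed in patients who took up ALTA, not what PF did for the practice's eligible patients.

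The difference matters for an implementation strategy. A practice that reaches few eligible patients has delivered little of the intended benefit, but a participants-only BP estimate does not show it. The plan expects incomplete reach: Section 6.1.4 tracks missed opportunities, and Section 6.3.5 plans interviews with 60 patients who decline. BP control is also the outcome on which the trial is powered, so its population should not be left to inference.

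**Working it through.** **1. The plan's own power figure.** Section 6.4.2 gives 10 sites, 700 patients, ICC 0.01 to 0.05, at least 80% power for 15 points and over 90% for 20 points. Section 6.4.3.2 gives the test: "All tests will be two-sided with $\alpha=0.05$ for comparison between the implementation and UC phases". The usual-care rate, the number of periods and the patients per cluster-period are not stated. Assumptions: usual-care rate 29% (the former trial's rate quoted in 6.4.2); 5 cohorts (Figure 1) of 2 sites, giving 6 periods; 700/(10 × 6) = 11.67 patients per cluster-period.

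The Hussey-Hughes variance is

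Var = Iσ²(σ² + Tτ²) / {(IU − W)σ² + (U² + ITU − TW − IV)τ²}

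with I = 10, T = 6, U = 30, W = 220, V = 110. So IU − W = 80, and the second bracket is 900 + 1800 − 1320 − 1100 = 280. For 29% to 44%, the mean rate is 0.365 and s² = 0.365 × 0.635 = 0.2318. Then τ² = ICC × s² and σ² = (1 − ICC) × s²/11.67.

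- ICC 0.01: τ² = 0.00232, σ² = 0.01967, Var = 0.00660/2.222 = 0.00297, SE = 0.0545. Power = Φ(0.15/0.0545 − 1.96) = 79%.
- ICC 0.05: τ² = 0.01159, σ² = 0.01887, Var = 0.01668/4.755 = 0.00351, SE = 0.0592. Power = Φ(0.15/0.0592 − 1.96) = 72%.

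Other binomial variance choices raise these to at most 83% and 77%. For 20 points the ranges are 95-97% and 92-95%, in line with the plan. A usual-care rate of 20% gives 84% and 78% for 15 points. With 35 or more patients per cluster-period, power for 15 points is about 99% or higher. The 80% floor is therefore met under some readings and narrowly missed under others. The point made here does not depend on it.

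**2. Who is analysed: the passages side by side.**

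| Place | Points to |
|---|---|
| 6.4.2 | 700 recruited patients; does not say who they are |
| Synopsis | n=700 as ALTA participants |
| 6.3.4 | 70 per clinic (70 × 10 = 700), drawn from ALTA-exposed patients, for surveys on tertiary outcomes |
| 5.2.2 and 6.3.6 | BP extracted by research assistants; at 12 months "trained RAs will repeat the chart review procedures for consenting patients" |
| 6.1.1 | eligible patients recruited in usual care |
| 6.1.4 | EHR report on hypertensive patients of the sites, to be de-identified and analysed in aggregate for the primary outcome |
| 6.4.3.2 | person-level model with a person random effect; no population, no mention of the report |

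An ALTA-exposed sampling list cannot exist while a site is in usual care, so 6.1.1 and 6.3.4 cannot both describe the same sample. The only number tied to BP control is 700, and the only descriptions of 700 are of ALTA-exposed patients. That is the best-supported reading, though nowhere stated.

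**3. What it could do to the effect.** Let u be the share of eligible patients who take part, and assume non-participants gain nothing. Then effect in eligible patients = u × effect in participants.

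| u (assumed) | 15 points becomes | 20 points becomes | Power for diluted 15 points, 700 in total, ICC 0.01 / 0.05 |
|---|---|---|---|
| 0.9 | 13.5 | 18 | 70% / 63% |
| 0.7 | 10.5 | 14 | 50% / 44% |
| 0.5 | 7.5 | 10 | 29% / 25% |

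The power column holds the total at 700. Analysing all eligible patients would raise it by an amount the documents do not give. With 70 per cluster-period, the same three effects have power of about 100%, 99% and 85-87%.

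**The case against.** The strongest reply is that the 700 are a survey sample. Section 6.3.4 ties the 70 per clinic to tertiary outcomes, Section 6.1.4 takes BP and PDC from an EHR report on the practices' hypertensive patients, and the eligibility criteria do not require ALTA participation. This stands as far as it shows that the documents conflict. It does not settle the matter, because the report is described as aggregate and for the primary outcome, whereas 6.4.3.2 needs patient-level data.

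A reader might infer that the plan claims an intent-to-treat result while excluding non-participants, and that PF is overstated by a definite share, such as 30% from the 700:300 split. The documents do not support that:
- The intent-to-treat wording ("the resulting F-test will provide the primary" test) is in 6.4.3.1, in the model linking fidelity to clinical outcomes. Section 6.4.3.2 does not use the term.
- Consent in 6.3.6 is to the evaluation, not to ALTA. Section 6.3.2 has a single form for both groups, so this passage does not exclude non-participants.
- Section 6.4.3.3 also analyses SBP, DBP and PDC, so the 300 cannot be said to serve the relationship outcomes alone.
- The model compares each person before and after. If the same participants supply both readings, the filter applies to both phases and stable motivation is largely shared. A between-phase selection bias in favour of PF is therefore not shown. What remains is the narrower target population.
- 700 and 300 are planned sample sizes, not an uptake rate.
- PF redesigns the whole practice, and Section 3.3.1 expects benefit to spread to new patients, so zero gain in non-participants is only an assumption.

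Reach is also measured elsewhere, in the dose domain of the primary outcome. That is fair, but it does not put reach into the BP and PDC estimates.

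**Conclusion.** The concern holds in this form. The population for BP control and PDC is undefined, and the passages that bear on it conflict. Following the Synopsis and Sections 6.3.4 and 6.4.2 as written gives an effect among ALTA participants selected after crossover. Section 5.1 asks for the effect of PF on eligible patients of the randomised practices.

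The participants' result is likely to exceed the practice-level effect on two conditions: uptake below 100%, and less benefit in non-participants. The plan anticipates the first; the second is plausible but not documented. The size is unknown because no uptake is given. The figures of 13.5, 10.5 and 7.5 points are illustrations at assumed uptakes with no gain in non-participants; any such gain would narrow the gap. This is an improvement worth making before analysis, not a demonstrated overstatement.

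**What to change.** In Section 6.4.3.2, define the primary population for BP control and PDC as all patients of each practice who meet the EHR-based ALTA clinical criteria, applied by the same rule in each phase. Analyse them by the practice's randomised phase whether or not they joined ALTA, using a patient-level version of the EHR extract described in Section 6.1.4. Report the participants-only result as supportive and label it the effect among participants. Keep the 700 and 300 consented patients for the survey outcomes. Reconcile the roles of the 700, 500 and 300 figures, and recruitment in usual care (6.1.1) with sampling from exposed patients (6.3.4). Restate power for the chosen population, giving the usual-care rate, the period structure and an assumed uptake.

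Costs: a person-level extract in place of an aggregate report, possibly an IRB modification, missing survey covariates for patients who did not consent, and probably a smaller reported effect. The extract already planned holds BP readings and PDC, and the sites can already identify eligible patients who were not enrolled.

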6.4.3.1 Primary Analyses

General procedures for analysis of our primary outcome: We will use a mixed methods approach to assess the five core dimensions of implementation fidelity, as defined by Proctor's IOF: (1) adherence to the program protocol; (2) dose of the program delivered; (3) quality of program delivery; (4) participant responsiveness; and (5) program differentiation.

Our qualitative analysis of implementation fidelity will be comprised of practice facilitator narrative reports (to assess program adherence), audiotaped health coaching sessions (to assess implementation quality) and semi-structured interviews with clinic staff/providers and patients (to assess participant responsiveness). Transcriptions of the narrative reports and interviews will be coded using Atlas.ti, software designed for qualitative coding. The coding scheme will be developed by the Data Management and Analysis Subcommittee to focus on key dimensions identified both a priori (i.e., from the interview protocols) and those that emerge during site visits and interviews. The study team members coding the transcripts will

be rigorously trained on both the coding scheme and on the use of Atlas.ti. Initial coding by the coders will be reviewed by either [name] or [name] and any corrections to the coding will be made and/or additional coder training. Following this period, two coders will independently code at least 10 interviews. At this point we will establish the inter-rater reliability and if it is inadequate (Krippendorff's $\alpha < 0.80$) the Data Management and Analysis Subcommittee will work collaboratively to refine and/or clarify the coding scheme and provide additional coder training. Double coding will continue until adequate inter-rater reliability is achieved. Coding the data will allow us to fully describe the themes and the prevalence of specific themes and sub-themes. Following the procedures in our previous trials (e.g., ALMA trial), we will audiotape and archive MA-led health coaching sessions, of which 10% will be coded using the Health Coaching Evaluation Checklist. The checklist assesses the degree to which the MAs are correctly using their coaching techniques and are achieving the desired impact with patients. We will apply the same coding methods as the narrative reports and interviews. Briefly, two members of the study team will be rigorously trained by the Data Management and Analysis Subcommittee to apply the checklist to the tapes, and supervised by [name]. The coders will listen to the audiotapes twice, the first review will be done to get a sense of the session flow and MA counseling style; the second to code the interaction. We will establish inter-rater reliability after the two coders independently code at least 10 tapes, and double coding will continue until adequate inter-rater reliability is achieved (Krippendorff's $\alpha > 0.80$).

Level of implementation adherence will be evaluated quantitatively as the degree to which the components of ALTA (e.g., identify, refer, coach, document, monitor) were implemented as intended, using data from checklists completed by the facilitators as well as extracted from the EHR. Each intervention component will be rated on a 3-point scale: 1=The component was not implemented, as per protocol; 2=The component was partially implemented; and 3=The component was fully implemented and/or modified with permission, as per protocol. We will calculate adherence as the number of components fully implemented (ratings of 3) divided by the total number of possible components ($N=8$). Practices will be considered adherent to the protocol if components were implemented completely and/or they were completed with an adaption that did not affect the programs core components and was approved by the study team. Facilitators will also complete monthly narrative reports that summarize all adaptations made to the components and what did/did not work for each practice context. We will also measure adherence through the Health Coaching Evaluation Checklist. The checklist will be used to count the parts of the standardized counseling script that were covered by the MAs at each health coaching session.

Part 2.

- Level of Implementation dose will be evaluated as the extent to which patients were exposed to ALTA. We will collect data on utilization patterns of the different ALTA components including the mean number of: ALTA-eligible patients identified in the registry and referred to a Health Coach; health coaching sessions completed with ALTA patients; entries in the EHR-embedded coaching script; progress notes

documented in the EHR and shared with the care team; and follow-up sessions that are scheduled and/or completed. System files will be extracted quarterly and will contain date and time stamps as well as user logins for the tools used. We will also calculate the average program dose, which is defined as all the number of times the MA-led health coaching sessions occurred during the implementation phase divided by the total number of patient encounters at the clinic during that same period of time (i.e., 12 months). To compare average dose across the practices, we will use a least square means analysis of variance (ANOVA) model with weighting by the number of patients seen in each practice within the specified time period.

- Level of Implementation quality of each ALTA component will be evaluated as the quality and content of data entry in the HTN registry, EHR-embedded coaching script, progress notes, and follow-up scheduling. Facilitators will rate the completeness of this form using a 3-point rating scale (1, poor; 2, adequate; 3, high). A random 10% sample of counseling sessions by the clinic Health Coaches will also be audiotaped and evaluated using the Health Coaching Evaluation Checklist, as we have done in our previous trials. A fidelity score will be calculated as the percentage of topics completed and how well they were delivered (1: poor skill performance, 2: adequate skill performance, 3: exemplary skill performance).
- Level of responsiveness will be evaluated as patient and clinic staff/provider satisfaction with ALTA and acceptability for practice changes with validated measures (i.e., ECHO survey for patients and a modified survey developed by Lewis et al. for staff/providers). For both staff/provider and patient measures, we will calculate means and standard deviations for each scale across respondents within the practice. In addition, qualitative interviews will be conducted with a random sample of clinic staff (n=30) and patients (n=30) across the practices to assess satisfaction with the intervention. To compare responses across the practices, we will use a least square means ANOVA model with weighting by the number of respondents in each practice.
- Level of program differentiation will be evaluated as the unique features of ALTA that are distinguishable from other programs at the sites. Throughout the study, facilitators will catalogue all initiatives that are occurring at the practices (as observed during site visits and/or reported by the practice leadership). This will be used to quantify the degree of overlap between the ALTA components and other quality improvement initiatives at the sites (1: no overlap, 2: some overlap, 3: significant overlap as well as isolate the unique features of ALTA that distinguish it from those initiatives).

Following the NIH Best Practices for mixed methods research, we will construct a joint display that integrates the qualitative themes with the quantitative data to create a composite measure of implementation fidelity based on the five dimensions outlined above. Should the data be divergent, we will assign higher credence to the qualitative data because it provides richer explanation about participants' behaviors. We will also explore the association between implementation fidelity and the clinical outcomes. This analysis will be accomplished with a multilevel MANOVA (unstructured covariance matrix across two time points: baseline and 12 months). The analysis will have one within person factor — Time (baseline and 12-month coded naturally as months (0 and 12)) and one primary between-

patient factor (Randomization Group dummy coded as 0 = UC and 1 = PF). We will use the composite measure of implementation fidelity to predict changes in BP control and medication adherence at 12 months. We will use a 3-level analytic model to accounting for nesting in the data (observations nested within subjects nested within practices). Multilevel modeling software (SAS, Version 9, PROC MIXED) will be used to compute full information maximum likelihood (FIML) estimates of the model parameters. The PROC MIXED procedure will use an error structure that allows for the possibility of group differences in (a) the error variances at 12 months; and (b) the serial correlations of the baseline with the 12 month outcomes. The primary test is the treatment X time interaction, and the resulting F-test will provide the primary "intent to treat" test of the hypothesis. If this is statistically significant at the two tailed $\alpha=.05$ level, for ease of interpretation, we will estimate and report the magnitude of the treatment effect, with 95% CI for fidelity. Covariates will be included as necessary in adjusted analyses. All tests will be 2-sided, 0.05 level tests.

